### Liver Function Abnormalities

Liver function tests should be obtained before initiation of regorafenib and monitored at least every 2 weeks during first 2 months of treatment. Thereafter liver function should be monitored monthly or more frequently as clinically indicated.

For subjects with observed worsening of serum liver tests considered related to regorafenib (i.e. where no alternative cause is evident, such as post-hepatitis cholestasis or disease progression), the dose modification and monitoring advice in the table below should be followed.

Regorafenib is a UGT1A1 inhibitor. Mild, indirect (unconjugated) hyperbilirubinemia may occur in subjects with Gilbert's syndrome.

Dose Modification/interruption for alanine aminotransferase and/or aspartate aminotransferase increases related to study drug			
Increases in AST/ALT (per NCI CTCAE v 4)	1st Occurrence	Restart	Recurrence
AST and/or ALT < 5 X ULN (<Grade 3)	Continue dosing, with weekly monitoring of liver function until transaminases return to < 3 X ULN (< Grade 1) or baseline.		
ALT and/or AST > 5 X ULN (> Grade 3)	Interrupt dosing, with weekly monitoring until transaminases return to < 3 X ULN or baseline.	If the potential benefit of reinitiating regorafenib is considered to outweigh the risk of hepatotoxicity: reduce 1 dose level and measure serum transaminases weekly for at least 4 weeks.	Discontinue
ALT and/or AST > 20 X ULN (> Grade 4)	Discontinue		
ALT and/or AST > 3 X ULN (> Grade 2) with concurrent bilirubin > 2 X ULN	Discontinue treatment and measure serum transaminases weekly until resolution. Exception: subjects with Gilbert's syndrome who develop elevated transaminases should be managed as per the recommendations outlined above for ALT/AST elevations.		

### **5.2.3 Prevention/Management Strategies for Diarrhea**

Diarrhea can be a common side effect of regorafenib. The preventive/management strategies for diarrhea should be consistent with local standards (e.g., antidiarrheals and optimized hydration status).

Anti-diarrhea medications may be introduced if symptoms occur. Previous trials have shown that the diarrhea could be managed with loperamide. The recommended dose of loperamide is 4 mg at first onset, followed by 2 mg every 2 to 4 hours until diarrhea-free for 12 hours.

## **6 TREATMENT DISCONTINUATION**

### **6.2 Reasons for Discontinuing Study Drug**

In the absence of treatment delays due to adverse events, treatment may continue for up to 2 cycles or until one of the following criteria applies:

- Disease progression
- Intercurrent illness that prevents further administration of study drug
- Unacceptable adverse event(s)
- Subject decides to withdraw from the study
- General or specific changes in the subject's condition render the subject unacceptable for further treatment in the judgment of the site investigator

### 6.3 Reasons for Withdrawal from Study

Subjects must be withdrawn from the trial (treatment and procedures) for the following reasons:

- Subject withdraws consent from study treatment and study procedures. A subject must be removed from the trial at his/her own request or at the request of his/her legally acceptable representative. At any time during the trial and without giving reasons, a subject may decline to participate further. The subject will not suffer any disadvantage as a result.
- Pregnancy. Pregnancy will be reported as an SAE. (Note: subjects who have been withdrawn from treatment with study drug because of pregnancy should not undergo CT scans [with contrast]/MRI or bone scans while pregnant.)
- If, in the site investigator's opinion, continuation of the trial would be harmful to the subject's well-being.
- Subject is lost to follow-up.
- Death.

Subjects **may be** withdrawn from the study for the following reasons:

- The subject is non-compliant with study drug, trial procedures, or both; including the use of anti-cancer therapy not prescribed by the study protocol.
- Severe allergic reaction to regorafenib (such as exfoliative erythroderma or Grade 3 or 4 hypersensitivity reaction) or ginseng.
- The development of a second cancer.
- Development of an intercurrent illness or situation which would, in the judgment of the site investigator, significantly affect assessments of clinical status and trial endpoints.
- Deterioration of ECOG performance status to 4.
- Use of illicit drugs or other substances that may, in the opinion of the site investigator, have a reasonable chance of contributing to toxicity or otherwise skewing trial result.

Any subject removed from the trial will remain under medical supervision until discharge or transfer is medically acceptable.

In all cases, the reason for withdrawal must be recorded in the eCRF and in the subject's medical records.

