### 2.2. Secondary Objectives

- 1) Assess the difference in adherence to regorafenib between the two groups. Pill counts will be used to assess adherence. The hypothesis is that Ginseng may increase adherence by decreasing fatigue.
- 2) Assess the difference in toxicities between the two arms.
- 3) Assess the difference in retention between the two arms. Retention is the proportion of subjects who complete the study. Note that they may not completely adhere to the study medication, but as long as they come in for the last measurements, they are considered retained.
- 4) Assess response rate and overall survival

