## **Treatment compliance**

An adequate record of receipt, distribution, and return of all study drugs must be kept in the form of a Drug Accountability Form.

Subject compliance with the treatment and protocol includes willingness to comply with all aspects of the protocol, and to have blood collected for all safety evaluations. At the discretion of the site investigator, a subject may be discontinued from the trial for non-compliance with follow-up visits or study drug.

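### Investigator withdrawal for non-compliance or endpoint-affecting illness conflicts with the retention definition and can cost later fatigue and pill-count data

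*Combined protocol and SAP*

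**What the plan says.** Section 6.3 has two lists. The mandatory list opens "Subjects must be withdrawn from the trial (treatment and procedures) for the following reasons" and includes the investigator's opinion that continuing would harm the subject. The optional list concerns withdrawal from the study. One of its reasons reads "The subject is non-compliant with study drug, trial procedures, or both". Another is an illness or situation that would, "in the judgment of the site investigator, significantly affect assessments of clinical status and trial endpoints". The section ends by requiring that "the reason for withdrawal must be recorded in the eCRF and in the subject's medical records".

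The Treatment compliance paragraph of Section 9 says that, at the site investigator's discretion, "a subject may be discontinued from the trial for non-compliance with follow-up visits or study drug".

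Three other places bear on the same subjects:

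- Section 2.2, item 3, defines retention as completing the study and says of subjects that "they may not completely adhere to the study medication, but as long as they come in for the last measurements, they are considered retained".
- Section 6.2 lists reasons for stopping study drug, among them "Intercurrent illness that prevents further administration of study drug" and unacceptable adverse events.
- Footnote 7 to the Section 7 calendar asks for an end-of-treatment (EOT) visit 30 days after stopping, for anyone who stops before finishing cycle 2. Section 7.3 puts the fatigue questionnaires and a pill count at that visit. Footnote 8 provides three-monthly follow-up, which Section 7.4 limits to progression, further cancer treatment and survival.

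Section 2.3 names fatigue score, adherence, toxicity and retention as the endpoints. Section 11 says the retention and adherence estimates can be used to size further work. It gives no rule for subjects withdrawn by the investigator, no missing-data method and no dropout allowance.

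**The concern.** The optional reasons overlap with what the trial measures. Non-compliance with study drug is close to the adherence endpoint, and an illness that affects the endpoints is likely to affect fatigue. If either leads to removal from the study, later data are missing for a reason tied to the outcome.

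The decision is discretionary and is made knowing the arm. Section 5 gives controls no ginseng, and no placebo product is described; the word placebo in the synopsis sample-size text appears to be a leftover. If study drug covers both products named in Section 9, a ginseng subject has two products to be non-compliant with and a control subject has one.

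At stake are the two estimates meant to inform the next trial, adherence and retention, and to a lesser degree the fatigue difference, which Section 11 will read against bands of 8 to 12 and of 12 or more.

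**Working it through.** **1. The plan's own figures.** The documents give no withdrawal, dropout or adherence rate, so there is no planned figure on this point to reproduce. The sample-size figures in Section 11, which assume that all 90 subjects are analysed, do reproduce. The half-width is 1.96 × 27.0 × √(1/60 + 1/30) = 11.83 (stated 11.833). Satterthwaite power for a difference of 17, with SDs of 27.0 and 26.1, is 80.9% (stated 80%).

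**2. The same subject under different provisions.**

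- A subject takes too few tablets but is willing to attend. Under Section 2.2 the subject attends and is retained. Under Section 6.3 or the Section 9 paragraph the site may withdraw the subject, who then does not attend and is not retained. The behaviour is the same and the endpoint value differs.
- A subject's illness stops study drug in cycle 1. Under Section 6.2 with footnote 7 the subject has an EOT visit with questionnaires and pill count. Under the illness item of Section 6.3 the subject leaves the study, and nothing says that the EOT visit still applies.

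**3. What is lost, by timing.** Section 5 places pill counts at cycle 2 day 1 and EOT only. Section 11 puts the primary contrast at the end of cycle 1.

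- Non-compliance found by pill count is first visible at cycle 2 day 1. The cycle 1 count and the questionnaires are due at that visit. Withdrawal then costs the later questionnaires and the second count.
- Withdrawal during cycle 1, for illness or self-reported non-compliance, precedes any scheduled count and the primary time point. Section 1 reports that most adverse events on regorafenib came in cycles 1 and 2, so illness that early is plausible.

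**4. Retention.** One withdrawal of a subject who would have attended lowers retention by 1/30 = 3.3 points in control and by 1/60 = 1.7 points in ginseng.

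**5. Adherence (illustration).** Assume 70% true adherence in the ginseng arm: 42 of 60 adherent and 18 not. Assume also that withdrawn non-adherent subjects leave the denominator.

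- 3 withdrawn: 42/57 = 73.7%
- 6 withdrawn: 42/54 = 77.8%
- 9 withdrawn: 42/51 = 82.4%

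The gain is 3.7 to 12.4 points. If the same subjects are kept and scored out of the planned days, the rate stays at 42/60 = 70%.

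A between-arm bias needs unequal removal. With 70% in control (21 of 30), withdrawing 3 of its 9 non-adherent subjects gives 21/27 = 77.8%, the same as 6 of 18 in ginseng, so the difference is zero. If 6 leave in ginseng and none in control, a false difference of 77.8 − 70.0 = 7.8 points appears.

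**6. Fatigue (illustration).** If a share w of an arm is missing and its mean differs by g from that of the rest, the observed mean moves by w × g. With w of 10% to 20% and g of 10 to 20 points, the shift runs from 0.10 × 10 = 1 to 0.20 × 20 = 4 points. This is a complete-case approximation. The repeated-measures model would recover part of it from earlier scores.

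**7. Precision (illustration).** Losing 10% of both arms before the primary contrast (54 and 27 left) gives a half-width of 1.96 × 27 × √(1/54 + 1/27) = 12.47 and power of 76.5%. Losing 20% (48 and 24 left) gives 13.23 and 71.3%.

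**The case against.** The strongest case on the other side has five parts.

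- Section 2.2 is conditional on attendance and Section 6.3 is permissive, so a site can obey both. That is right: this is a conflict of purpose, not a logical impossibility. It still leaves the retention value to the site's choice.
- The words about treatment and procedures attach to the mandatory list only, and footnotes 7 and 8 can be read to cover subjects on the optional list. That reading is available. However, footnote 7 is triggered by stopping treatment and is silent on subjects removed from the study, while footnote 8 collects no fatigue score or pill count. That both readings are open is itself the defect.
- A reader might infer that Section 6.3 deletes the adherence, retention and fatigue outcomes. The documents do not support this. Scores taken before withdrawal stay in the repeated-measures model, and non-compliance found at cycle 2 day 1 comes to light when the cycle 1 count and the primary fatigue value are due. A withdrawn subject would naturally count as a drop-out in the Kaplan-Meier analysis of retention.
- The adherence illustration depends on its denominator. Section 11 scores each subject's pills out of 21 and does not exclude withdrawn subjects, so the inflation occurs only if they are dropped or have no count. This stands, and it is why the fix states the scoring.
- Withdrawal is optional, its reason is recorded, and some listed reasons, such as a second cancer or an allergic reaction, are not endpoints here. This also stands and makes a sensitivity analysis possible. A recorded reason does not recover data that were never collected.

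**Conclusion.** The point holds in a limited form. Sections 6.3 and 9 let a site that knows the arm end a subject's participation for reasons close to the endpoints. Section 2.2 would keep a non-adherent subject, and Section 6.2 with footnote 7 would keep an assessment visit for a subject who stops drug early. No text says which governs or how such subjects are analysed. Retention is the endpoint most directly affected, followed by cycle 2 adherence and later fatigue scores. The primary contrast is exposed only to withdrawals before the end of cycle 1.

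The size is not known. The adherence range of 73.7% to 82.4% rests on an assumed 70% rate and removal from the denominator. The fatigue shift of 1 to 4 points rests on assumed shares and differences. A reader might take these as expected biases, or infer that the rule favours ginseng. The documents support neither, since they give no withdrawal rate by arm and equal proportional removal would leave the adherence difference unchanged. The change is worth making because it prevents outcome-related missing data at little cost; the ambiguity does not by itself invalidate the trial.

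**What to change.** - In Section 6.3 and the Treatment compliance paragraph of Section 9, separate stopping study treatment from withdrawal from study assessments.
- State that subjects taken off treatment by the investigator, including for non-compliance, who still consent keep the already scheduled questionnaires, pill count, EOT visit and survival follow-up. Say whether this includes the cycle 2 day 1 assessments for someone who stops in cycle 1, since footnote 7 mentions only the EOT visit.
- Reconcile Sections 6.2, 6.3 and 9 and footnote 7 with the retention definition in Section 2.2.
- In Section 11, analyse these subjects in their randomised arm, score adherence out of the planned days, and say how an investigator-initiated withdrawal enters the retention and fatigue analyses. The recorded reasons allow a sensitivity analysis.

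The clinical reasons for stopping treatment, including pregnancy and investigator-judged harm, are for the sponsor to reconcile. Nothing here asks for them to be added, removed or moved.

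The cost is wording in a few sections, with no new procedures. The downside is that sites must keep assessing a few uncooperative or ill subjects. Footnote 8 allows telephone contact for survival follow-up, but footnote 6 places the questionnaires and pill counts in clinic, so some of these data will still be missing.

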## 7 STUDY SCHEDULE OF EVENTS

Cycle = 28 days

Examination	Screening		Cycle 1		Cycle 2		After completion of Cycle 2	End of Treatment Visit 	Follow up 
	-28 days	-7 days	Day 1	Day 15 (±3)	Day 1 (±3)	Day 15 (±3)	(±5)	30 days (± 7) after last dose of Cycle 2	(±7)
REQUIRED ASSESSMENTS									
Informed Consent	X								
Medical history	X								
Height	X								
Physical examination	X		X	X	X	X		X	
Vital signs including BP, weight and ECOG performance status	X	X 	X	X	X	X		X	
CBC w/ differential		X		X	X	X		X	
Complete Metabolic Profile 		X		X	X	X		X	
PT/INR and aPTT 		X	[D5]		[X]			X	
Pregnancy test 		X							
Urinalysis 		X	X		X				
AEs & concomitant medications	X		X	X	X	X		X	
DISEASE ASSESSMENT									
Pathology Review	X								
CT chest/abdomen/pelvis 	X						X 		
TREATMENT									
Regorafenib 			X	X	X	X			
Ginseng 			X	X	X	X			
OTHER									
MFSI-SF, PROMIS 			X		X 			X	
Pill count 					X			X	
FOLLOW-UP									
For progression, start of additional cancer treatment, and survival									X

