7. The End of Treatment visit should occur 30 days after completion of Cycle 2 ( $\pm$  7 days). Subjects who stop treatment prior to completion of Cycle 2 should have the EOT 30 days after discontinuation of treatment. Subjects who have an ongoing  $\geq$  grade 2 or serious AE (SAE) at this visit will continue to be followed until the AE resolves to  $\leq$  Grade 1 or baseline, deemed clinically insignificant, and/or until a new anti-cancer treatment starts, whichever is earlier.
8. Follow up will occur in all subjects after completion of Cycle 2 every 3 months for 18 months. Follow up may be accomplished via clinic visit, phone call, or other avenues as appropriate.
9. Day -7 only ECOG performance status need be obtained.
10. Urinalysis should be done if proteinuria is suspected as per site investigator's discretion.

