## **7.3 End of Treatment: At least 30 days ( $\pm 7$ ) after the last dose of Cycle 2**

- Complete physical examination
- Vital signs including BP, weight and ECOG performance status
- Laboratory testing:
  - Complete Blood Count (CBC) with differential and platelet count??
  - Complete metabolic profile (CMP)
  - PT/INR and aPTT
- Adverse event and concomitant medication assessment
- Administer MFSI-SF and PROMIS questionnaires
- Pill count

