## **7.4 Follow-Up ( $\pm 7$ )**

Subjects will be followed every 3 months for 18 months after completion of Cycle 2:

- Disease progression
- Type and start date of additional cancer treatment
- Survival status

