## **10.2 Adverse Event Reporting**

### **10.2.1 Site Requirements for Recording Adverse Events**

Adverse events (AEs) will be recorded from the time of consent and for 30 days after the last dose of study drugs, regardless of whether or not the event(s) are considered related to the study drugs. The descriptions and grading scales found in the revised NCI Common Terminology

Criteria for Adverse Events (CTCAE) v4 will be utilized for AE reporting. A copy of the CTCAE v4 can be downloaded from the CTEP website at <http://ctep.cancer.gov>.

All AEs considered related to study drug will be followed until resolution, return to baseline, or deemed clinically insignificant, even if this occurs post-trial.

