#### **10.2.2 Site Requirements for Reporting Serious Adverse Events to HCRN**

Site investigators and other site personnel must report any SAEs occurring from the time of informed consent to 30 days after the last dose of study drugs. This includes events both related and unrelated to the study drugs.

The definition of “related” being that there is a reasonable possibility the drug caused the adverse experience.

Unrelated	The Adverse Event is clearly not related to the study drug(s)
Unlikely	The Adverse Event is doubtfully related to the study drug (s)
Possible	The Adverse Event may be related to the study drug (s)
Probable	The Adverse Event is likely related to the study drug (s)
Definite	The Adverse Event is clearly related to the study drug (s)

The completed SAE Submission Form (see SPM) must be sent to HCRN **within 24 hours** of discovery of the event. The form may be sent to HCRN either electronically to [[contact]](mailto:[contact]) or by fax to [contact]. The site investigator is responsible for informing the IRB and/or the Regulatory Authority of the SAE as per local requirements.

The original copy of the SAE Submission Form and the fax confirmation sheet/email must be kept within the site study file.

Follow-up information should be submitted to HCRN either electronically to [[contact]](mailto:[contact]) or by fax to [contact], using a SAE Submission Form stating that this is a follow-up to the previously reported SAE and providing the follow-up number if appropriate. Each re-occurrence, complication, or progression of the original event should be reported as a follow-up to that event regardless of when it occurs. The follow-up information should describe whether the event has resolved or continues, if and how it was treated, and whether the subject continued or withdrew from study participation.

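### The End of Treatment visit is timed in three ways that disagree, and its minus-7 side lets the last scheduled adverse event check fall up to 7 days before the 30-day capture period ends

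*Combined protocol and SAP*

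**What the plan says.** The timing of the End of Treatment visit is stated in three places:

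- The schedule of events in Section 7 has "30 days (± 7) after last dose of Cycle 2".
- Footnote 7 to that schedule has "The End of Treatment visit should occur 30 days after completion of Cycle 2", with ± 7 days. For subjects who stop early it says that they "should have the EOT 30 days after discontinuation of treatment", and that sentence gives no window.
- Section 7.3 is headed "End of Treatment: At least 30 days", followed by ± 7 and counted from the last dose of Cycle 2.

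The capture period is stated separately. Under Section 10.2.1 adverse events "will be recorded from the time of consent and for 30 days after the last dose of study drugs", whether or not they are thought related. Under Section 10.2.2 sites "must report any SAEs occurring from the time of informed consent to 30 days after the last dose of study drugs".

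After the End of Treatment visit, Section 7.4 says: "Subjects will be followed every 3 months for 18 months after completion of Cycle 2". The items listed there, and in the follow-up column of the schedule, are progression, further cancer treatment and survival. Adverse events are not among them.

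**The concern.** Two stated rules do not fit together. The capture rule runs to day 30 after the last dose. The visit rule lets the last scheduled adverse event assessment fall on day 23. Section 7.3 also conflicts with itself, because a minimum of 30 days cannot stand beside an allowance of 7 days fewer. A site reading the three statements cannot tell which starting point applies or whether day 30 is a floor.

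The visit also decides later follow-up. Footnote 7 continues to follow Grade 2 or higher events and serious events that are ongoing at the visit. An event that begins after an early visit cannot be ongoing at it, and no later contact is scheduled to find it.

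The difference in toxicity between arms is a secondary objective (Section 2.2), compared with Fisher exact tests (Section 11). The end of scheduled ascertainment for that comparison would depend on when the visit was booked and on which starting point the site used.

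**Working it through.** This is calendar arithmetic for a subject who completes both cycles without delay. Day 1 is Cycle 1 Day 1, so Cycle 2 runs from day 29 to day 56. The last dose of Cycle 2 is taken to be the last dose of whichever study drug the subject takes latest.

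**Inputs**
- Regorafenib is taken on Days 1–21 of each cycle (Section 5.1, Table 1), so the last dose is day 28 + 21 = 49.
- Ginseng is taken on every day of each cycle (footnote 5 to the schedule), so the last dose is day 28 + 28 = 56.
- Completion of Cycle 2 is day 56.
- Visit window: 30 ± 7 days from the starting point.
- Capture period: 30 days after the last dose of study drugs.

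**Formulas**
- Earliest visit = starting point + 30 − 7.
- Days without a scheduled assessment = the larger of 0 and 30 − (visit day − last dose day).

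**Earliest permitted visit**

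| Starting point | Arm | Visit window (study days) | Earliest visit, days after last dose | Days not covered |
|---|---|---|---|---|
| Last dose (schedule) | Regorafenib only | 72–86 | 72 − 49 = 23 | 7 |
| Last dose (schedule) | Ginseng | 79–93 | 79 − 56 = 23 | 7 |
| Completion of Cycle 2 (footnote 7) | Regorafenib only | 79–93 | 79 − 49 = 30 | 0 |
| Completion of Cycle 2 (footnote 7) | Ginseng | 79–93 | 79 − 56 = 23 | 7 |

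The largest gap is 7 of 30 days, and 7/30 = 23%. A visit on the nominal date or later leaves 0 days uncovered in every row.

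**Which drug the uncovered days follow.** In the ginseng arm the earliest visit, day 79, is 79 − 49 = 30 days after the last regorafenib dose. Regorafenib's own 30 days are therefore covered there, and the uncovered days count from ginseng only. Under footnote 7 the same holds for regorafenib in the control arm, so that arm has no gap.

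**Next contact.** The first follow-up comes about three months after Cycle 2. Taking that as 91 days gives about day 56 + 91 = 147 (± 7), well after the capture period has closed.

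**The case against.** The strongest reply is that nothing stops at the visit. The duty in Sections 10.2.1 and 10.2.2 runs to day 30 whenever the visit is held. Serious events must be reported within 24 hours of discovery, by whatever route they come to light. Monitors compare source documents with submitted data (Section 12.3). Related events are followed to resolution even after the trial (Section 10.2.1). All of this stands. A reader might infer that up to a week goes unassessed, or that events in it are found only if the subject volunteers them. The documents support only that those days have no scheduled assessment.

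The reply does not remove the mismatch. The continuing follow-up concerns events already known, and no contact is scheduled to find new ones. Section 5.2 asks for adverse event evaluation at each study visit, but the schedule and Section 7.4 assign none to follow-up, which may be a phone call.

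A second reply is that Section 7.3, read literally, already sets a floor of 30 days. It may show the intent, but the same heading keeps the ± 7, and neither the schedule nor footnote 7 has a floor.

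A reader might also infer that the toxicity comparison is biased between arms. The documents do not show that. Under the schedule's starting point the maximum gap is 7 days in both arms. Under footnote 7 both arms are seen on the same study days and regorafenib's 30 days are covered in each. Section 11 does not tie the comparison to the visit date, and no event count can be derived for the affected days.

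**Conclusion.** The concern holds as a minor inconsistency. The three timing statements need to be reconciled with each other and with the 30-day capture period. For subjects who complete Cycle 2 and are seen before post-dose day 30, at most 7 of the 30 required days (23%) have no scheduled adverse event assessment. Under footnote 7's starting point this affects the ginseng arm alone, and only days counted from ginseng.

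The figures assume dosing on schedule. They do not extend to early stoppers, for whom footnote 7 gives 30 days without a stated minus side. How many visits would be held early, and how many events would begin in those days, cannot be known from the documents.

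**What to change.** Use one rule in the schedule column, footnote 7 and Section 7.3, with a window that cannot open before the capture period closes and with the same starting point in both arms. Suggested wording: 30 days (+7) after completion of Cycle 2; for subjects who stop early, 30 days (+7) after the last dose of any study drug. The word *any* matters because Section 5.2.2.1 lets the other study treatment continue when regorafenib is discontinued. For on-schedule completers the visit then falls on study days 86–93 in both arms, which is 30–37 days after ginseng and 37–44 days after regorafenib. The largest gap falls from 7 days to 0. Onset dates should be recorded so that events in controls after post-dose day 30 can be told apart from those inside the capture period.

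Counting +7 from the last dose in everyone would also close the gap, but visits would fall on days 79–86 in controls and 86–93 in the ginseng arm. That would build a one-week difference between arms into a visit that also carries MFSI-SF and PROMIS.

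Alternatively, keep a ± 7 window under one reconciled starting point and, whenever the visit falls before post-dose day 30, ask the adverse event questions by phone on or after day 30. This leaves the fatigue assessments where they are.

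Cost of the first option: a wording change in three places and a narrower booking window (8 days instead of 15). Some visits and their fatigue forms move later and further from the week-8 assessment named in Section 11. The shift is at most 86 − 72 = 14 days, for controls now booked from the last regorafenib dose, and at most 86 − 79 = 7 days otherwise. Cost of the second: a short call for subjects seen early. Neither touches the primary contrast, which Section 11 places at the end of Cycle 1.
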